#### **Angiographic Exclusion Criteria**

20. Failure to treat clinically significant inflow lesions in the ipsilateral iliac, femoral, or popliteal arteries with ≤30% residual stenosis, and no serious angiographic complications (e.g., embolism).
21. Failure to successfully treat significant *non-target* infra-popliteal lesions prior to treatment of *target* lesion(s). Successful treatment is defined as obtaining ≤50% residual stenosis with no serious angiographic complications (e.g., embolism).
22. Treatment of vessels below the ankle joint.
23. Failed pre-dilatation in *target* lesion during index procedure with angiographic evidence of serious angiographic complications.
24. Target lesion includes in-stent restenosis.
25. Evidence of aneurysm or thrombus in target vessel.
26. No calcium or mild calcium in the target lesion.
27. Target lesion within native or synthetic vessel grafts.

	No.: CP 65007	REV. C
	TITLE: Disrupt PAD BTK II Study	
	CLASS: CLINICAL PROTOCOL	PAGE 26 OF 71

28. Failure to successfully cross the guidewire across the target lesion; successful crossing defined as tip of the guidewire distal to the target lesion in the absence of flow limiting dissections or perforations.

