### 7.2 Subject Selection

Subjects who meet the clinical inclusion/exclusion criteria will undergo an angiogram performed according to the institution's standard of care. If all angiographic eligibility criteria are met, the subject is considered to be enrolled once the peripheral IVL catheter has been inserted over a 0.014" guidewire that crossed the target lesion. A subject is considered an angiographic screen failure if they do not meet angiographic eligibility criteria. Subjects who screen fail will be documented as such in the electronic data capture (EDC) system.

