### 7.2.2 Exclusion Criteria

Subjects who meet any of the following exclusion criteria may not be enrolled in the study:

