### 7.7.1 Procedural Imaging Requirements

An angiographic cine will be obtained for each lesion treated including pre-procedure, post-IVL and end of procedure. (If any non-target lesions are treated, an additional cine will be obtained prior to IVL treatment of any target lesion(s) to ensure no serious angiographic complications have occurred and that the subject still meets criteria to be enrolled.) All angiographic images must be submitted to the core lab for analysis. If intravascular imaging (i.e., IVUS) is performed, images from the three timepoints (baseline, immediately post-IVL, and end of procedure) should be submitted to the IVUS core lab for analysis.

	No.: CP 65007	REV. C
	TITLE: Disrupt PAD BTK II Study	
	CLASS: CLINICAL PROTOCOL	PAGE 31 OF 71

For subjects enrolled in the IVUS Sub-study, angiographic and IVUS images are required at three (3) timepoints: baseline, immediately post-IVL, and end of procedure. The core lab will provide separate angio and IVUS protocols to participating study centers.

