#### **7.7.3 Treatment of Non-Target Lesions**

Non-target lesions must be treated successfully prior to treatment of the target lesion(s). After the maximum number (2) of target lesions has been reached, any additional lesions should be assigned as non-target lesions. Non-target lesions may be treated with any commercially available device; treating a non-target lesion with a device that is not approved or considered investigational will result in a protocol deviation.

*Note: In the case where non-target lesions and target lesion are present in both limbs, non-target lesions should be treated successfully first per limb.*

Clinically significant inflow lesions in the ipsilateral iliac, femoral, or popliteal arteries must be treated with  $\leq 30\%$  residual stenosis and no serious angiographic complications (e.g., embolism). Significant non-target infra-popliteal lesions must be treated with  $\leq 50\%$  residual stenosis with no serious angiographic complications (e.g., embolism). If there are serious angiographic complications following treatment of non-target lesions, the subject should not be enrolled.

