#### **7.7.5 Definition of Enrollment**

The definition of enrollment is when the subject signs informed consent, meets all general & angiographic eligibility criteria, and the IVL catheter has been inserted over a 0.014" guidewire (which had been previously passed across the target lesion).

	No.: CP 65007	REV. C
	TITLE: Disrupt PAD BTK II Study	
	CLASS: CLINICAL PROTOCOL	PAGE 32 OF 71

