### 7.7.6 Pre-IVL Dilatation (if required)

If the operator is unable to pass the IVL balloon across the lesion, a standard PTA balloon up to 2.5mm should be used for pre-dilatation prior to treatment with the IVL Balloon (not applicable for enrollment of non-dilatable lesions).

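### Does a serious complication during pre-dilatation, after the IVL catheter has gone in, turn an enrolled subject into a screen failure and take them out of the ITT set?

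*Combined protocol and SAP*

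**What the plan says.** The exclusion list opens with the rule "Subjects who meet any of the following exclusion criteria may not be enrolled in the study". Item 23 on it is "Failed pre-dilatation in *target* lesion during index procedure with angiographic evidence of serious angiographic complications". Neither the item nor section 15.1 says what counts as a failed pre-dilatation, and the item is not limited to the time before the IVL catheter is inserted.

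Enrolment is defined twice. Section 7.2 says that, once the angiographic criteria are met, "the subject is considered to be enrolled once the peripheral IVL catheter has been inserted over a" guidewire that has crossed the target lesion. Section 7.7.5 requires that the subject has consented, "meets all general & angiographic eligibility criteria, and the IVL catheter has been inserted over a" guidewire. Section 7.2 adds: "A subject is considered an angiographic screen failure if they do not meet angiographic eligibility criteria".

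Section 7.7.6 describes pre-dilatation: "If the operator is unable to pass the IVL balloon across the lesion, a standard PTA balloon up to 2.5mm should be used". It states that this step does not apply to enrolling non-dilatable lesions. Those are covered by inclusion criterion 12c, which requires a balloon angioplasty attempt during the index procedure that leaves more than 50% stenosis and causes no serious angiographic complication.

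Section 7.7.7 keeps a subject enrolled in two cases: a crossing failure with no pulses (exit after discharge), and incomplete crossing with pulses (follow-up to 24 months). Section 9.4 defines ITT as all enrolled subjects. Section 7.9 lists newly developed exclusion criteria among the potential reasons for withdrawal.

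**The concern.** Read literally, the order of steps is awkward. Insertion marks enrolment, and the pre-dilatation of section 7.7.6 follows insertion. A complication at that step could meet an exclusion criterion in a subject who is already enrolled. The screen-failure sentence in section 7.2 has no time limit, and section 7.7.5 makes meeting all criteria part of enrolment itself.

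For non-target lesions the plan is more careful. Section 7.7.1 asks for an extra cine before IVL to confirm "that the subject still meets criteria to be enrolled", and section 7.7.3 says: "If there are serious angiographic complications following treatment of non-target lesions, the subject should not be enrolled". Exclusion 23 has no such anchor. Section 7.7.7 settles the uncrossed lesion, but no sentence covers a lesion that is crossed after a complicated pre-dilatation.

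Serious angiographic complications are a component of the primary effectiveness endpoint (section 9.2.2). A site that logged such a subject as a screen failure would remove a likely failure for a reason tied to the outcome, and adverse event collection, which runs from enrolment (section 10.4.1), would lose its basis. Withdrawal under section 7.9 would keep the subject in ITT but could lose the 30-day safety assessment, which would then leave the denominator (sections 9.1 and 9.5).

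**Working it through.** **Reading the passages in time order**

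| Step | Where | Status that follows |
|---|---|---|
| Balloon attempt to show the lesion is non-dilatable | Inclusion 12c | Not yet enrolled; a serious complication means 12c is not met |
| Criteria met, guidewire across, IVL catheter inserted | 7.2, 7.7.5 | Enrolled |
| IVL balloon will not pass, so pre-dilatation | 7.7.6 | Enrolled; nothing reverses it |
| Still not crossed, no pulses | 7.7.7 | Expressly enrolled |
| Not fully crossed, pulses given | 7.7.7 | Expressly enrolled |
| Crossed after pre-dilatation | No express sentence | Enrolled at insertion, hence ITT under 9.4 |

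1. The last row follows from the second. It is also a stronger case for inclusion than the two rows above it, where the plan keeps the subject although treatment was incomplete or absent.
2. Exclusion 23 has work to do before enrolment. Criterion 12c admits a lesion after an unsuccessful balloon attempt without serious complications; exclusion 23 bars one after an unsuccessful attempt with them. The plan does not call the 12c attempt pre-dilatation, so this is a reading, but it reconciles the exclusion list with the definition of enrolment.
3. Section 7.7.6 dilatation is done so that the IVL balloon can pass. If the balloon then passes, it is not obvious that the dilatation failed, so the unsettled case may be almost empty.

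**Planned precision, used as the yardstick (section 9.3)**

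Inputs: n = 225, success 75.8%, precision ±5.8 points, 10% loss.

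- 0.758 × 225 = 170.55, taken as 171. The exact 95% interval for 171/225 = 76.0% is 69.87% to 81.43%, so the half-width is (81.43 − 69.87)/2 = 5.78 points, which agrees with ±5.8.
- 225/0.9 = 250, as stated.
- The stated width probability of 0.827 is reproduced with the Wald interval (0.8273), but not with the exact interval (0.509). That is a separate matter and does not bear on this point.

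**Effect of a misreading**

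If k failures leave a set of N with S successes, the rate rises by S/(N − k) − S/N = S·k/[N(N − k)]. Take N = 250 and S = 190 (0.758 × 250 = 189.5). The values of k are assumptions.

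| k removed | Rate (exact 95% interval) | Rise, points | Share of 5.8 |
|---|---|---|---|
| 0 | 190/250 = 76.00% (70.21–81.16) | – | – |
| 1 | 190/249 = 76.31% (70.53–81.45) | 0.31 | 5% |
| 2 | 190/248 = 76.61% (70.84–81.74) | 0.61 | 11% |
| 3 | 190/247 = 76.92% (71.16–82.03) | 0.92 | 16% |
| 4 | 190/246 = 77.24% | 1.24 | 21% |

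- Near the 99% lesion-level result quoted in section 3.1.2: 247/250 = 98.80% becomes 247/249 = 99.20%, a rise of 0.40 points for one subject.
- Outer case, k = 8 (8/250 = 3.2% of subjects), with all eight counted as failures if kept: 183/250 = 73.2% against 183/242 = 75.6%, a difference of 2.4 points; near 99%, 240/250 = 96.0% against 240/242 = 99.2%, a difference of 3.2 points.
- If the complication had resolved and the subject was a success, removal gives 189/249 = 75.90%, a fall of 0.10 points.
- Safety, assuming three 30-day events and losing the subject with one of them: 3/250 = 1.20% (0.25–3.47) becomes 2/249 = 0.80% (0.10–2.87), a fall of 0.4 points.

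**The case for a change.** The best case for a change is that up to 40 sites apply the text, and sites do not reason by inference as a statistician does. A coordinator who sees exclusion 23 met could log a screen failure under section 7.2. Keeping the subject might instead look like a deviation from the exclusion criteria, which section 12.3 classes as major. The error would mostly run one way, towards a higher success rate, in a single-arm study whose only inference is an estimate and its interval. One sentence would settle it.

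Part of this stands. No sentence says that enrolment at insertion cannot be undone, the key word in exclusion 23 is undefined, and its text is not confined to the pre-enrolment period. The answer follows from the passages together and is not stated in any one of them.

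The rest is weaker. The screen-failure sentence in section 7.2 contrasts candidates who do not qualify with those who do and are then enrolled; it is not a rule for un-enrolling anyone. The opening rule of the exclusion list also looks forward to enrolment. The withdrawal route in section 7.9 is general and optional. It leaves the subject in ITT, section 7.7.1 still sends the end-of-procedure cine to the core lab, and section 7.9.1 allows earlier data to be kept. What could be lost is later follow-up, as with any withdrawal.

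**Conclusion.** No change to the plan follows. This is missing detail that analysts would fill in one sensible way: the subject was enrolled at catheter insertion, belongs to the ITT cohort, and is scored on the core-lab reading at the final timepoint. An added sentence would only write down that answer. It would be a harmless optional clarification at the next amendment, limited to classification and analysis; the clinical scope of exclusion 23 and of withdrawal is for the sponsor.

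The effect is small even if a site misreads the text: 0.3 to 0.4 points on procedure success for each removed failure, with four needed to exceed one point near the planning rate, against ±5.8 points. It is nil or slightly in the other direction if the complication has resolved by the final timepoint. No hypothesis test is affected (section 2.0), and the sample size does not move.

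This rests on assumed counts, since the documents give no rate of complicated pre-dilatation. Section 3.1.2 reports no serious complications at the end of the procedure among 101 patients, which suggests few cases, but section 3.2 indicates that use of adjunctive therapy was less limited in that cohort. Figure 2 and any separate SAP text were not available and may already settle the order of steps.

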## 7.3 Informed Consent

Prior to undergoing any study-specific tests or procedures, the subject or their legally designated representative must sign and date the site's current and approved Institutional Review Board (IRB)/Ethics Committee (EC) informed consent form (ICF) in order to be eligible for study participation. The informed consent must contain all elements required by 21 CFR Part 50, EU MDR 2017/745 Article 63, and ISO 14155:2020 and comply with the ethical principles of the Declaration of Helsinki.

### 7.3.1 Process for Obtaining Informed Consent

The process for obtaining informed consent is outlined below:

- The Investigator or his/her authorized designee conducts the informed consent process
- All aspects of the clinical study that are relevant to the subject's decision to participate will be included in the consent form
- Investigators will avoid any coercion or undue improper influence on, or inducement of, the subject to participate
- The consent process shall not waive or appear to waive the subject's legal rights
- The consent must use native non-technical language that is understandable to the subject
- The Investigator or designee will provide ample time for the subject to read and understand the informed consent form and to consider participation in the clinical investigation
- The consent must include personally dated signatures of the subject and the Investigator, or an authorized designee responsible for conducting the informed consent process, and/or all signatures required by the reviewing IRB/EC
- The Investigator or designee will provide the subject with a copy of the signed and dated informed consent form and any other written information

### 7.3.2 Subjects Needing Legally Designated Representative

Informed consent may be given by a legally designated representative only if a subject is unable to make the decision to participate in a clinical study. In such cases, the subject shall also be informed about the clinical study within his/her ability to understand.

Please follow the local IRB/EC guidelines on this process.

	No.: CP 65007	REV. C
	TITLE: Disrupt PAD BTK II Study	
	CLASS: CLINICAL PROTOCOL	PAGE 27 OF 71

### 7.3.3 Subjects Unable to Read or Write

Informed consent shall be obtained through a supervised oral process if a subject or legally designated representative is unable to read or write, if allowed by the IRB/EC. An independent witness shall be present throughout the process. The written informed consent form and any other information shall be explained to the prospective subject or his/her legally designated representative and, whenever possible, either shall sign and personally date the informed consent form. The witness also signs and personally dates the informed consent form attesting that the information was accurately explained, and that informed consent was freely given.

### 7.3.4 Addition of New Information

Shockwave Medical will revise the written informed consent form whenever new information becomes available that may be relevant to the subject's confirmed participation in the clinical study. The revised information will be sent to the Investigator for approval by the IRB/EC. After approval by the IRB/EC, a copy of this information must be provided to the participating subjects, and the informed consent process as described above needs to be repeated.

Please follow the local IRB/EC guidelines on the process of re-consenting subjects.

## 7.4 Schedule of Events and Evaluations

Table 1 lists the schedule of events and evaluations required for the study.

**Table 1. Schedule of Events and Evaluations**

Assessment	Screening / Baseline	Enrollment and Procedure	Discharge 	30 Days (±7 days)	6 Months (180±30 days)	12 Months (365±30 days)	24 Months (730±30 days)	TLR
Eligibility	✓							
Informed Consent 	✓							
Medical History	✓							
Physical Exam	✓			✓	✓	✓	✓	
Baseline Labs (eGFR)	✓							

	No.: CP 65007	REV. C
	TITLE: Disrupt PAD BTK II Study	
	CLASS: CLINICAL PROTOCOL	

Assessment	Screening / Baseline	Enrollment and Procedure	Discharge 	30 Days (±7 days)	6 Months (180±30 days)	12 Months (365±30 days)	24 Months (730±30 days)	TLR
Pregnancy Test	✓							
Ankle-Brachial Index/Toe-Brachial Index (ABI/TBI)	✓ 			✓	✓	✓	✓	
Rutherford Category (RC)	✓			✓	✓	✓	✓	
VascuQoL-6 Questionnaire	✓			✓	✓	✓	✓	
Wound Healing Assessment (including photographs)	✓ 			✓	✓	✓	✓	
Medications (anticoagulants & antiplatelets)	✓	✓	✓	✓	✓	✓	✓	
Angiogram		✓						✓ 
IVUS (sub-study)		✓ 						
Duplex Ultrasound (DUS)					✓ 	✓ 		

	No.: CP 65007	REV. C
	TITLE: Disrupt PAD BTK II Study	
	CLASS: CLINICAL PROTOCOL	

Assessment	Screening / Baseline	Enrollment and Procedure	Discharge 	30 Days (±7 days)	6 Months (180±30 days)	12 Months (365±30 days)	24 Months (730±30 days)	TLR
Adverse Events		✓	✓	✓	✓	✓	✓	✓

TLR = target lesion revascularization; DUS = duplex ultrasound; ABI = ankle-brachial index; TBI = toe-brachial index; QoL = quality of life

1. Consent to be obtained within 30 days prior to procedure.
2. Within 60 days prior to procedure.
3. For the IVUS Sub-study, IVUS imaging is required at baseline, immediately post-IVL, and end of procedure.
4. Within 12-24 hours post procedure or prior to hospital discharge, whichever occurs first.
5. Angiographic images acquired as standard of care prior to the TLR should be submitted to the core lab.
6. Within 45 days of procedure.
7. In the event of a non-diagnostic DUS, a 90-day extension is allowed on the upper limit of the window for the 6- and 12-month visits.

## 7.5 Medications

Anticoagulation/antiplatelet medications should be administered according to the 2017 European Society of Cardiology (ESC) and European Society of Vascular Surgery (ESVS) PAD guidelines [19] and the 2016 American College of Cardiology (ACC) and American Heart Association (AHA) PAD guidelines [5].

Additional recommendations for anticoagulation and antiplatelet medications include:

- Unfractionated heparin dosing should be undertaken according to hospital standard of care.
- Prasugrel or ticagrelor may be used as an alternative to clopidogrel for existing management of acute coronary syndrome (ACS).
- Follow antiplatelet and anticoagulation guidelines for the management of patients with atrial fibrillation.

## 7.6 Screening/Baseline Procedures

Baseline assessments must be completed within 30 days of the procedure. The following are exceptions: wound assessment which can be completed within 45 days of procedure, ankle-brachial index (ABI) / toe-brachial index (TBI), which can be completed within 60 days of the procedure, and a pregnancy test which must be done within 7 days of the procedure. Informed consent must be obtained prior to any study-specific evaluations needed to assess eligibility which are not considered standard of care. Subjects on warfarin or direct thrombin inhibitors should be followed per institutional standard of care by the physician.

Baseline assessments include:

- Medical history
- Physical examination

	No.: CP 65007	REV. C
	TITLE: Disrupt PAD BTK II Study	
	CLASS: CLINICAL PROTOCOL	PAGE 30 OF 71

- Vital signs
- Height and weight
- Baseline Labs (eGFR)
- ABI or TBI (at rest; use same test for subject throughout study)
- Rutherford Category
- VascuQoL-6 Questionnaire
- Wound Healing Assessment (including photographs)
- Review of medications (anticoagulants and antiplatelets)
- Urine pregnancy test if female of child-bearing age

*Note: If treatment of two target lesions is planned across both limbs, the RC category and ABI/TBI for each limb must be assessed. If ABI/TBI cannot be assessed due to non-compressible vessels, this should be documented. If TBI is used, subject should have TBI at each follow-up visit.*

eGFR should be calculated using the CKD-EPI formula in absence of a standardized lab test provided by the site.

Wound healing assessments of the target limb(s) must be performed at baseline and all follow-up visits. Photographs must be taken of the wound(s) to document the progression of wound healing throughout the study and kept in the subject's study binder. Photographs will be retained at the site in the study subject's medical record but will not be provided to the Study Sponsor via upload. If photographs are not obtained, a protocol deviation will be issued. At the follow-up visits, the wounds will be recorded in the EDC as healed (completely epithelialized), not healed, recurrent, new, or amputated. If the wound is not healed, it will be further classified as improving, stagnant, or worsening. A wound can only be considered recurrent if it was healed at a prior study visit and subsequently re-appears at the same location.

